2.7. SUBGROUPS

Subgroup analysis on selected efficacy endpoints will be conducted by

- R-ISS for MM (stage I, II, and III respectively)
- Region (US vs. non-US).
- FLC MM patient (yes vs. no), a FLC MM patient is defined as a patient without measurable disease in SPEP or UPEP, but with measurable disease in FLC, all based on baseline value.
- Prior daratumumab alone or in combination
 - ever received daratumumab in a combination therapy vs. as single agent ± dexamethasone

- received daratumumab in last line prior treatment (in combination therapy or as single agent ± dexamethasone) vs. did not receive daratumumab in last line prior treatment

2.8. POOLING OF CENTERS FOR STATISTICAL ANALYSES

All participating centers in the study will be pooled together for analysis.

2.9. COMPUTING AND CODING STANDARDS

Activities will be performed using the following tools:

Table, listing, and figure production	SAS Version 9.4 or higher
Coding	
AEs	MedDRA Version 20.1
Medical Histories	MedDRA Version 20.1
Prior and Concomitant Medications	WHO DDE Version March 2017
Grading	
AEs	CTCAE Version 4.0
Labs	CTCAE Version 4.03

3. PATIENT INFORMATION

3.1. DISPOSITION OF PATIENTS AND ANALYSIS POPULATIONS

This study consists of two parts. Part 1 (Protocol v1.0-3.0) enrolled patients with both quad-refractory MM and penta-refractory MM. Part 2 (Protocol v \geq 4.0) enroll patients with penta-refractory MM only.

Patient disposition will be summarized for Part 1 and Part 2 patients separately. Patient study status will be summarized in each of the following categories:

- Screened patients, defined as any patient who has signed the informed consent form
- Patients who met study eligibility criteria (including patients who did not meet all eligibility criteria per the protocol in effect at the time of enrollment but received waiver from Sponsor) but did not receive any dose of study treatment (partial or complete)
- Patients who met study eligibility criteria (including patients who did not meet all eligibility criteria per the protocol in effect at the time of enrollment but received waiver from Sponsor) and received at least one dose of study treatment (partial or complete)
- An end-of-treatment disposition:
 - Patients who were still on treatment
 - Patients who discontinued treatment and primary reason for treatment discontinuation
- An end-of-study disposition:
 - Patients who were still on study
 - Patients who withdrew from study and primary reason for study withdrawal

3.1.1. Efficacy Populations

The primary efficacy populations will only include patients from Part 2. Results for Part 1 patients will be summarized and analyzed separately.

The ***modified intent-to-treat (mITT) population*** will consist of Part 2 patients with penta-refractory MM who met all eligibility criteria (or did not meet all eligibility criteria but received waiver from Sponsor to enter the study), and received at least one dose of study treatment (partial or complete). This population will include patients who have discontinued therapy due to toxicity or PD and patients who have died from any cause, including those related to study treatment or disease. The mITT population will be used for the primary efficacy analyses.

The ***BCLPD-ref population*** will consist of patients in Part 2 who had MM *documented* to be refractory to bortezomib, carfilzomib, lenalidomide, pomalidomide, and daratumumab, and received at least one dose of study treatment (partial or complete).

The ***CLPD-ref population*** will consist of patients in Part 2 who had MM *documented* to be refractory to carfilzomib, lenalidomide, pomalidomide, and daratumumab, and received at least one dose of study treatment (partial or complete).

The **BCPD-ref population** will consist of patients in Part 2 who had MM *documented* to be refractory to bortezomib, carfilzomib, pomalidomide, and daratumumab, and received at least one dose of study treatment (partial or complete).

The **CPD-ref population** will consist of patients in Part 2 who had MM *documented* to be refractory to carfilzomib, pomalidomide, and daratumumab, and received at least one dose of study treatment (partial or complete). Note that this population has MM that is refractory to both second generation IMiDs (pomalidomide) and proteasome inhibitor (carfilzomib), as well as daratumumab.

The BCLPD-ref, CLPD-ref, BCPD-ref, CPD-ref populations will be used for supportive inferences concerning efficacy.

A patient is claimed to have documented refractory to a therapy if one of the following criteria is met:

- Best response on the therapy is SD or worse
- Patient progressed or relapsed during treatment
- Patient progressed or relapsed within 60 days after discontinuing this therapy.

If the date of treatment discontinuation or the date of disease progression/relapse is missing (partially or completely), unless it can be determined that one of the above criteria is met (e.g., both dates have day missing, but have the same year and month), the patient is determined to not have documented refractory.

3.1.2. Safety Population

The safety population will consist of all patients from Part 1 and Part 2, who have received at least one dose of study treatment (partial or complete) and have any post-baseline safety information.

Safety outputs will be presented by the following groups:

- Overall safety population
- The subset of safety population from Part 2
- The subset of safety population from Part 1

3.1.3. Additional Analysis Populations

Analysis of selected efficacy endpoints will be conducted in the following populations respectively:

The **All Penta-ref** population will consist of all patients from mITT (Part 2) and all Part 1 patients with penta-refractory MM who met all eligibility criteria (or did not meet all eligibility criteria but received waiver from Sponsor to enter the study), and received at least one dose of study treatment (partial or complete).

The **high-risk population** will consist of all Part 2 patients with penta-refractory MM with any of the following high-risk chromosomal abnormalities including del (17p)/p53, t(14; 16), t(4; 14), and 1q21, and received at least one dose of study treatment (partial or complete).

Chromosomal abnormalities are determined by the FISH test. If adequate test results from a central laboratory are available, such results will be used to determine the chromosomal abnormality status; otherwise, test results from the local site's laboratory will be used. If local laboratory results are not available either, FISH results from initial diagnosis (Disease History eCRF page) will be used if available. In the absence of test results indicating abnormality, a patient will be classified as normal for the corresponding mutation.

The ***Efficacy-Evaluable (EE) population*** will consist of all patients in the mITT population with at least one adequate post-baseline IRC-based MM response assessment.

The ***per-protocol (PP) population*** will consist of all patients in the mITT population who meet the following criteria:

- Have selinexor compliance $\geq 70\%$, see Section 3.4.2 for the definition of selinexor compliance rate.
- Have at least one adequate post-baseline response assessment unless died or withdrew from study before that.

The ***Part 1 quad-ref MM population*** (Part 1 – Quad) will consist of all quad-refractory patients in Part 1 who received at least one dose of study treatment (partial or complete).

The ***Part 1 penta-ref MM population*** (Part 1 – Penta) will consist of all penta-refractory patients in Part 1 who received at least one dose of study treatment (partial or complete).

Selected safety endpoints will be summarized within the Part 1 - Quad and Part 1 - Penta, populations respectively.

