4. EFFICACY

Patient response at each time point will be assessed centrally by an IRC according to the IMWG response criteria (*Kumar 2016*) for MM. Unless otherwise specified, MM response assessment refers to assessment determined by IRC. The primary endpoint (ORR) is based on these IRC assessed responses in the mITT population.

Documentation of response requires two consecutive readings of the applicable disease parameter (serum M-protein, urine M-protein, serum FLC, or quantitative immunoglobulin level), performed at any time with no minimum interval required between the two readings. The date of response or PD will be assigned to the earlier date of the two independent samples, unless PD is based on an unambiguous criterion such as a new plasmacytoma lesion.

If a patient had one PD assessment but was not subsequently confirmed, unless IRC considers the progression assessment unambiguous, it is not considered a PD (*Kumar 2016*).

Unless otherwise specified, efficacy analyses will use the mITT population. Analyses for the primary efficacy endpoint of ORR and the key secondary efficacy endpoints of DOR, CBR, and duration of clinical benefit will be repeated in the other efficacy populations and additional analysis populations. If relevant, selected efficacy analyses for other efficacy endpoints will be repeated in selected additional analysis populations.

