4.2.2.2. Analysis Methods

The rate of CBR and the 2-sided, exact 95% CI will be calculated using the mITT population. Median duration of clinical benefit with 95% CI will be estimated based on the Kaplan-Meier method. The Kaplan-Meier curve for the duration of clinical benefit will be provided.

As supportive analyses, CBR rate and 95% CI will be calculated:

- Using the BCLPD-ref, CLPD-ref, BCPD-ref, CPD-ref, all penta-ref, high-risk, EE, PP, Part 1 – Quad, Part 1 – Penta, doses populations respectively.
- In patients with R-ISS for MM stage I, II, and III respectively
- In US vs. non-US patients
- In FLC MM vs. non-FLC MM patients.

Median duration of clinical benefit with 95% CI will be calculated in these analysis populations and subgroups when sufficient data exist.

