4.2.7. Overall Survival (OS)

4.2.7.1. Definition

OS is defined as the duration from start of study treatment to death from any cause. If death event did not occur during the follow-up period, the patient is censored at the date of discontinuation from the study, or date of last participating visit (e.g., a telephone contact with patient status being alive), or database cut date, whichever is earlier.

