4.2.7.2. Analysis Methods

The proportion of patients with death event and the 2-sided, exact 95% CI will be calculated using the mITT population. Median OS time with 95% CI will be estimated based on the Kaplan-Meier method. The Kaplan-Meier curve for OS will be provided.

The following supportive OS analyses will be conducted:

- Using the BCLPD-ref, CLPD-ref, BCPD-ref, CPD-ref populations respectively
- Using the all penta-ref, high-risk, EE, PP, Part 1 – Quad, Part 1 – Penta, respectively, if sufficient data exist

- The same as in primary OS analysis except additional censoring at the start date of a new MM treatment
- In patients with R-ISS for MM stage I, II, and III respectively, if sufficient data exist
- In US vs. non-US patients, if sufficient data exist
- In FLC MM vs. non-FLC MM patients, if sufficient data exist
- In patients with a best response of confirmed PR or better
- In patients with a best response of confirmed MR or better
- In patients with a best response of confirmed MR
- In patients with a best response of SD or worse (including patients whose disease is not evaluable)

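### Overall survival is to be repeated in the Efficacy-Evaluable set, whose membership depends on an assessment after first dose, so that result is expected to be biased upward.

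*SAP*

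**What the plan says.** SAP 3.1.1 makes mITT the primary set: Part 2 penta-refractory patients who were eligible or waived and took at least one dose. It says of that set: "This population will include patients who have discontinued therapy due to toxicity or PD and patients who have died from any cause".

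SAP 3.1.3 adds the EE set, which "will consist of all patients in the mITT population with at least one adequate post-baseline IRC-based MM response assessment". The reason for a missing assessment plays no part. The per-protocol set, defined just after it, has a similar requirement with an exception: "Have at least one adequate post-baseline response assessment unless died or withdrew from study before that". SAP 1.7 records that clause as a deliberate change. SAP 1.8 records that EE was added in a revision of SAP version 1.0.

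EE is used as follows:

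- **OS.** SAP 4.2.7.1: "OS is defined as the duration from start of study treatment to death from any cause". SAP 4.2.7.2 then lists, where data suffice, supportive analyses "Using the all penta-ref, high-risk, EE, PP" and the two Part 1 sets.
- **ORR, DOR, CBR, duration of clinical benefit.** SAP section 4: "Analyses for the primary efficacy endpoint of ORR and the key secondary efficacy endpoints of DOR, CBR, and duration of clinical benefit will be repeated". The repeat extends to every additional population, and so to EE. SAP 4.2.2.2 also names EE for CBR. The detailed ORR list in SAP 4.1.3 is blacked out, but the general statement in section 4 covers it.

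**The concern.** OS needs no response assessment, so restricting it to assessed patients adds nothing to its measurement. It only changes who is counted, and it does so by an event that happens after the clock has started. A patient assessed on day 28 cannot have died on days 1 to 27. A patient who died on day 10 with no assessment is removed altogether. That is guaranteed (immortal) time, and nothing in SAP 4.2.7 corrects for it.

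For ORR and CBR the mechanism is simpler. A patient without an adequate IRC assessment cannot be a confirmed IRC responder, so EE removes non-responders only. The numerator stays and the denominator shrinks.

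At stake is how the supportive results are read. A reader who sees an EE median OS beside the mITT median may take the gap as information about the treatment, when some of it comes from the membership rule.

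**Working it through.** **1. The plan's own counts.** Protocol Table 3, penta-refractory row: VGPR 2 + PR 4 + MR 6 + SD 6 + PD 5 + NE 7 = 30. ORR = 6/30 = 20.0% and CBR = 12/30 = 40.0%, as printed. Overall row: 4 + 12 + 10 + 27 + 9 + 16 = 78, with ORR 16/78 = 20.5% (printed as 21%). Non-evaluable patients are therefore in the denominator as non-responders.

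**2. ORR and CBR with those patients removed.** With r responders, N treated and x unassessed, the EE rate is r/(N − x), which is at least r/N. Taking NE as a proxy for x:

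| Part 1 group | All patients | NE removed |
|---|---|---|
| Penta ORR | 6/30 = 20.0% | 6/23 = 26.1% |
| Penta CBR | 12/30 = 40.0% | 12/23 = 52.2% |
| Overall ORR | 16/78 = 20.5% | 16/62 = 25.8% |
| Overall CBR | 26/78 = 33.3% | 26/62 = 41.9% |

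The documents do not confirm that NE means no adequate assessment, so a range is needed. At the planned N = 122 (protocol synopsis, Study Numbers) with an assumed true mITT ORR of 20%, the expected number of responders is 0.20 × 122 = 24.4. With 6, 12, 26 or 28 patients unassessed (about 5%, 10%, 21%, 23%), the EE ORR is 24.4/116 = 21.0%, 24.4/110 = 22.2%, 24.4/96 = 25.4% or 24.4/94 = 26.0%.

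**3. When an assessment can first occur.** In protocol Table 1 and SAP Table 7-1, serum FLC is scheduled at C1D15. SPEP, UPEP, quantitative Ig and FLC are scheduled at C2D1 and at the End-of-Treatment visit within 14 days of the last dose. Day 15 and day 28 are therefore reasonable bounds for illustration.

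**4. OS shift.** The documents give no survival figures, so the medians here are assumptions. Let OS be exponential with median m, and let EE require survival to t0. Then:

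- Share dying before t0 = 1 − 2^(−t0/m).
- Median from first dose among those kept = m + t0, because the exponential has no memory.
- t0 = 15/30.4375 = 0.49 month, or 28/30.4375 = 0.92 month.

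| Assumed m (months) | Dead before day 15 | EE median | Dead before day 28 | EE median |
|---|---|---|---|---|
| 4 | 8.2% | 4.49 (+12%) | 14.7% | 4.92 (+23%) |
| 8 | 4.2% | 8.49 (+6%) | 7.7% | 8.92 (+12%) |
| 12 | 2.8% | 12.49 (+4%) | 5.2% | 12.92 (+8%) |

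The shift is about 0.5 to 0.9 month whatever the median, so it matters most when survival is short.

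**The case against.** Several points on the other side are sound.

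- **The schedule softens the gate.** A reader might infer that everyone who stops for toxicity or progression before C2D1 leaves EE. The documents do not support that. Full assessments are due at the End-of-Treatment visit, protocol Table 1 footnote 9 asks for a repeat at progression, and FLC is due at C1D15. Many such patients can still enter EE. Those reliably lost are patients who die or leave before any adequate assessment.
- **The OS bias is not a mathematical certainty.** A reader might say that EE OS must exceed mITT OS. EE also drops living patients who were never adequately assessed, and some of them may survive long. Upward bias is the expected direction, not a guaranteed one. A much larger shift would need a sizeable excluded group with very short survival, for which the documents give no figure.
- **No test is run in EE in the visible text.** A reader might infer an inflated chance of success against the 10% threshold. SAP 4.1.2 applies that rule to mITT only, and protocol 13.1.1 confines hypothesis testing to the primary endpoint.
- **Much is reported elsewhere.** Protocol 13.1.3 tabulates the number in each population and the number with non-evaluable disease, SAP 3.1 gives reasons for stopping treatment and study, and SAP 5.2 lists deaths.
- **EE is a conventional supportive set.** The per-protocol assessment criterion already keeps early deaths and withdrawals. Rewriting EE the same way would make it nearly mITT, so for ORR and CBR a new definition is a matter of preference.

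What remains after these points is OS in EE from first dose, which has no landmark and no stated purpose, and the need to label EE ORR and CBR.

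**Conclusion.** The point holds for OS. SAP 4.2.7.2 plans a survival analysis from first dose in a set chosen by a later event, and it is expected to be biased upward relative to mITT. The size is about 0.5 to 0.9 month on the median. This assumes exponential survival and that EE membership amounts to survival to day 15 or day 28. Earlier assessments would make the shift smaller.

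For ORR and CBR the direction is certain but the definition is acceptable for a supportive set. In Part 1 penta-refractory patients the gap would be 6.1 points for ORR (26.1 − 20.0) and 12.2 points for CBR (52.2 − 40.0). This takes NE as the proxy, from a cohort in which 51 of 78 patients had six rather than eight doses per cycle. A smaller unassessed share gives a smaller gap.

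A reader might infer that the trial's main claim is in doubt. It is not: the primary ORR analysis uses mITT, which keeps every treated patient who meets its definition, and EE OS is one supportive output among many, run only if data suffice.

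**What to change.** 1. Delete EE from the OS list in SAP 4.2.7.2. If OS in assessed patients is wanted, start it at a fixed landmark named in advance, for example the end of the C2D1 visit window. Include only patients who are alive and in follow-up at that point and already have an adequate assessment, and label the result as survival from the landmark.
2. Keep the EE definition for ORR and CBR if the sponsor wishes, but title those outputs as response among assessed patients. Place them beside the mITT estimates, with the number excluded and the reason for each exclusion (death, withdrawal, inadequate or missing assessment).

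The cost is one deletion or one added sentence in the SAP, plus a title and footnote on the EE tables. No new data are needed. The downside is that one supportive OS output is lost or changed.

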3.2. DEMOGRAPHICS AND BASELINE CHARACTERISTICS

In general, the baseline value is defined as latest value prior to the first dose of study treatment.

3.2.1. Demographic Data

Demographic variables include sex (female, male), race (American Indian or Alaska Native, Asian, Black or African American, Native Hawaiian or Other Pacific Islander, White, Other), ethnicity, and age at study entry.

3.2.2. Prior Therapies

Prior therapies for MM will be summarized with the following variables:

- Exposure/refractory status to each individual MM treatment including lenalidomide, pomalidomide, bortezomib, carfilzomib, and daratumumab, alkylating agent, glucocorticoid, anthracyclines, and stem cell transplant
- Refractory status to at least one IMiD, one PI, and daratumumab
- Refractory status to all five therapies including bortezomib, carfilzomib, lenalidomide, pomalidomide, and daratumumab
- Refractory status to all five therapies except bortezomib
- Refractory status to all five therapies except lenalidomide
- Refractory status to carfilzomib, pomalidomide, and daratumumab

- Number of prior systemic therapies (summarized as a continuous variable and as a categorical variable) and months from most recent prior systemic therapy to start of study treatment

The duration to be summarized is defined as follows.

- Months from most recent prior systemic therapy to start of study treatment will be calculated as (date of first dose of study treatment – stop date of most recent systemic therapy +1)/ (365.25/12).

3.2.3. Medical/surgical History

Medical/surgical history will be summarized in the mITT population by system organ class (SOC) and preferred term (PT) using the number and percentage of patients who had at least one occurrence of a SOC and PT. The summary will be sorted by alphabetic order in SOC, and further by decreasing frequency of PT within each SOC in the mITT population. When more than one PT has the same frequency, the order of presentation will be alphabetical in PTs.

3.2.4. Disease History

Disease history includes disease stage at initial diagnosis, disease stage at active myeloma, current disease stage according to ISS (or R-ISS if parameters available) for MM, and the following results at initial diagnosis: β_2 microglobulin, albumin, immunoglobulin type, light chain type, availability of bone marrow results, % plasma cells, and availability of FISH results. Smoking history including status (Never used, Current, Former), and frequency when applicable will also be recorded.

3.2.5. Physical Examination and Vital Signs

At screening, a full physical examination will be performed including height (without shoes) in centimeters (cm), weight (indoor clothing without shoes) in kilograms (kg), temperature, heart rate, systolic and diastolic blood pressure, and oxygen saturation. Significant findings that were present prior to the signing of informed consent must be included on the eCRF medical history page. Significant new findings, including the presence of plasmacytomas, that begin or worsen after informed consent must be recorded on the eCRF AE or Plasmacytoma page.

3.2.6. Eastern Cooperative Oncology Group (ECOG) Score

The ECOG performance status (Grade 0-5) will be recorded at screening.

3.2.7. Analysis Methods

Continuous data will be summarized using the number of available observations, mean, standard deviation, median, minimum, and maximum. Categorical and ordinal data will be summarized using the number and percentage of patients with the denominators for the percentages determined based on the analysis population used, unless otherwise specified. Demographics and baseline characteristics will be summarized among mITT, PP, BCLPD-ref, CLPD-ref, BCPD-ref, and CPD-ref populations respectively. P-values on demographic and baseline characteristic data will not be calculated. No specific description of the safety parameters will be provided at baseline. If relevant, the baseline values will be described along with each safety analysis.

